3.2. Recruitment and Retention

ADNI has a multi-faceted recruitment plan in place; the overall goal being to raise awareness of ADNI trials among targeted populations. ADNI will partner with NIA and coordinate with its ADEAR Center to take advantage of existing resources. The ADEAR center will also serve as the call center. In addition, a public relations/advertising firm will be consulted for broader coverage, and for seeking celebrity spokespersons and testimonies from other study participants or family members. ADNI will determine the special requirements of each site and pattern their individual public relations support around those needs. In that context ADNI will develop targeted messages in flyers, brochures, press releases, and presentations. Reference cards and online access to recruitment materials for the sites will also be available. Paid advertisements, direct mail and the Internet will be used as needed to supplement recruitment. A separate plan for minority recruitment is being developed. Enrollment will be monitored and tracked and additional support provided where appropriate. Additionally, ADNI will provide background to sites on how to reach target audiences as well as assist in identifying them. Technical assistance will be offered to the sites on an ongoing basis.

Several steps will be taken to assure the high follow up rate that is essential to the validity of the study results. All staff members will be carefully instructed regarding the need for an expectation of full follow up participation and the process of removing barriers to participation. At entry, each participant, and a significant other informant will be queried regarding plans to change residence or leave the area. It is recommended to maintain frequent contact with study participants as well as send thank you note following the clinical evaluation and a personalized greeting card on his or her birthday or on a major holiday to strengthen rapport and retention of study participants. Progress of the study may be placed in a newsletter, distributed to the sites, for distribution to study participants.

The goal of ADNI2 is to obtain as close to 100% participation in lumbar puncture as is feasible. ADNI1 aimed for 25% participation and achieved more than 50% participation. For ADNI2, recruitment will be limited to those that consent to LP. Exceptions can be requested from the Protocol PI and may be considered in order to meet other goals such as minority recruitment.

3.3. Data Collection and Monitoring

The Clinical Core will continue to be responsible for providing the operational infrastructure for this project, including the recruitment of approximately 650 additional subjects (150 cognitively normal, 100 subjects with significant memory concern, 100 with EMCI, 150 with LMCI, and 150 with AD, with a possibility of enrolling additional subjects should funding permit), as well as the longitudinal follow-up of all remaining ADNI-GO EMCI subjects and those subjects who originally enrolled in ADNI1 as cognitively normal and LMCI (regardless of whether a diagnostic conversion has occurred).

Clinical data collection and monitoring are standardized with well-established and successful ATRI operating procedures. Data will be entered directly by sites using web-based data entry screens. Imaging data collection and monitoring are handled by LONI. Imaging data are handled using a combination of data entry via web-based forms and automated file transition modules embedded within the web-based Image Data Archive application. The file translation modules

extract metadata directly from the imaging data, ensuring accuracy and reducing the amount of data entry required.

3.4. Data Sharing

In order to provide the clinical data from this project to Initiative investigators, the Pharmaceutical Industry and the public, the entire clinical database (free of any identifying information such as name, address, or phone number) will be placed on a public web site, which will be appropriately linked to the imaging database at LONI. The database will be frequently updated, and all clinical data acquired by the ADNI-CC will be provided in real-time.

4. Subject Selection

4.1 Inclusion Criteria: NEW Subjects – CN, SMC, EMCI, LMCI, AD

	CN	SMC	EMCI	LMCI	AD
1.	Subject must be free of memory complaints , verified by a study partner, beyond what one would expect for age	Subject must have a significant subjective memory concern as reported by subject, study partner, or clinician.	Subject must have a subjective memory concern as reported by subject, study partner, or clinician.	Same as EMCI	Same as EMCI
1a.	n/a	Significant memory concern confirmed by Cognitive Change Index score ≥ 16 (from the first 12 questions)	n/a	n/a	n/a
2.	Normal memory function documented by scoring above education adjusted cutoffs on the Logical Memory II subscale (Delayed Paragraph Recall, Paragraph A only) from the Wechsler Memory Scale – Revised (the maximum score is 25): a. ≥ 9 for 16 or more years of education b. ≥ 5 for 8-15 years of education c. ≥ 3 for 0-7 years of education	Same as CN	Abnormal memory function documented by scoring within the education adjusted ranges on the Logical Memory II subscale (Delayed Paragraph Recall, Paragraph A only) from the Wechsler Memory Scale – Revised (the maximum score is 25): a. 9-11 for 16 or more years of education b. 5-9 for 8-15 years of education c. 3-6 for 0-7 years of education	Abnormal memory function documented by scoring within the education adjusted ranges on the Logical Memory II subscale (Delayed Paragraph Recall, Paragraph A only) from the Wechsler Memory Scale – Revised (the maximum score is 25): a. ≤ 8 for 16 or more years of education b. ≤ 4 for 8-15 years of education c. ≤ 2 for 0-7 years of education	Same as LMCI
3.	Mini-Mental State Exam score between 24 and 30 (inclusive) (Exceptions may be made for subjects with less than 8 years	Same as CN	Same as CN	Same as CN	Mini-Mental State Exam score between 20 and 26 (inclusive) (Exceptions may be made for subjects with less than 8 years of education at the

	of education at the discretion of the project director)				discretion of the project director)
4.	Clinical Dementia Rating = 0 . Memory Box score must be 0	Same as CN	Clinical Dementia Rating = 0.5 . Memory Box score must be at least 0.5	Same as EMCI	Clinical Dementia Rating = 0.5 or 1.0
5.	Cognitively normal , based on an absence of significant impairment in cognitive functions or activities of daily living	Same as CN	General cognition and functional performance sufficiently preserved such that a diagnosis of Alzheimer's disease cannot be made by the site physician at the time of the screening visit	Same as EMCI	NINCDS/ADRDA criteria for probable AD

	CN	SMC	EMCI	LMCI	AD
6.	
Stability of Permitted Medications for 4 weeks. In particular, subjects may:
 
a. Take stable doses of antidepressants lacking significant anticholinergic side effects (if they are not currently depressed and do not have a history of major depression within the past 1 years)
 
b. Estrogen replacement therapy is permissible
 
c. Gingko biloba is permissible, but discouraged
 
d. Washout from psychoactive medication (e.g., excluded antidepressants, neuroleptics, chronic anxiolytics or sedative hypnotics, etc.) for at least 4 weeks prior to screening
	Same as CN	
Stability of Permitted Medications for 4 weeks. In particular, subjects may:
 
a. Take stable doses of antidepressants lacking significant anticholinergic side effects (if they are not currently depressed and do not have a history of major depression within the past 1 year)
 
b. Estrogen replacement therapy is permissible
 
c. Gingko biloba is permissible, but discouraged
 
d. Washout from psychoactive medication (e.g., excluded antidepressants, neuroleptics, chronic anxiolytics or sedative hypnotics, etc.) for at least 4 weeks prior to screening
 
e. Cholinesterase inhibitors and memantine are allowable if stable for 12 weeks prior to screen
	Same as EMCI	Same as EMCI

The following additional inclusion criteria apply to all diagnostic categories:

7. Geriatric Depression Scale less than 6.
8. Age between 55-90 (inclusive).
9. Study partner is available who has frequent contact with the subject (e.g. an average of 10 hours per week or more), and can accompany the subject to all clinic visits for the duration of the protocol.
10. Visual and auditory acuity adequate for neuropsychological testing.

11. Good general health with no diseases expected to interfere with the study.
12. Subject is not pregnant, lactating, or of childbearing potential (i.e. women must be two years post-menopausal or surgically sterile).
13. Willing and able to participate in a longitudinal imaging study.
14. Hachinski less than or equal to 4.
15. Completed six grades of education or has a good work history (sufficient to exclude mental retardation).
16. Must speak English or Spanish fluently.
17. Willing to undergo repeated MRIs (3Tesla) and at least two PET scans (one FDG and one Amyloid imaging) and no medical contraindications to MRI.
18. Agrees to collection of blood for GWAS, APOE testing and DNA and RNA banking.
19. Agrees to collection of blood for biomarker testing.
20. Agrees to at least one lumbar puncture for the collection of CSF.

4.2. Exclusion Criteria: NEW Subjects – CN, SMC, EMCI, LMCI, AD

	CN	SMC	EMCI	LMCI	AD
1.	Any significant neurologic disease, such as Parkinson’s disease, multi-infarct dementia, Huntington’s disease, normal pressure hydrocephalus, brain tumor, progressive supranuclear palsy, seizure disorder, subdural hematoma, multiple sclerosis, or history of significant head trauma followed by persistent neurologic defaults or known structural brain abnormalities	Same as CN	Any significant neurologic disease other than suspected incipient Alzheimer’s disease, such as Parkinson’s disease, multi-infarct dementia, Huntington’s disease, normal pressure hydrocephalus, brain tumor, progressive supranuclear palsy, seizure disorder, subdural hematoma, multiple sclerosis, or history of significant head trauma followed by persistent neurologic defaults or known structural brain abnormalities.	Same as EMCI	Any significant neurologic disease other than Alzheimer’s disease, such as Parkinson’s disease, multi-infarct dementia, Huntington’s disease, normal pressure hydrocephalus, brain tumor, progressive supranuclear palsy, seizure disorder, subdural hematoma, multiple sclerosis, or history of significant head trauma followed by persistent neurologic defaults or known structural brain abnormalities.

The following additional exclusion criteria apply to all diagnostic categories:

2. Screening/baseline MRI scan with evidence of infection, infarction, or other focal lesions. Subjects with multiple lacunes or lacunes in a critical memory structure are excluded.
3. Presence of pacemakers, aneurysm clips, artificial heart valves, ear implants, metal fragments or foreign objects in the eyes, skin or body.

4. Major depression, bipolar disorder as described in DSM-IV within the past 1 year. Psychotic features, agitation or behavioral problems within the last 3 months which could lead to difficulty complying with the protocol.
5. Currently treated with medication for obsessive-compulsive disorder or attention deficit disorder
6. History of schizophrenia (DSM IV criteria).
7. History of alcohol or substance abuse or dependence within the past 2 years (DSM IV criteria).
8. Any significant systemic illness or unstable medical condition which could lead to difficulty complying with the protocol.
9. Clinically significant abnormalities in B12, or TFTs that might interfere with the study. A low B12 is exclusionary, unless follow-up labs (homocysteine (HC) and methylmalonic acid (MMA)) indicate that it is not physiologically significant.
10. Residence in skilled nursing facility.
11. Current use of specific psychoactive medications (e.g., certain antidepressants, neuroleptics, chronic anxiolytics or sedative hypnotics, etc.). Current use of warfarin or dabigatran (exclusionary for lumbar puncture).
12. Current use of any other exclusionary medications
13. Investigational agents are prohibited one month prior to entry and for the duration of the trial.
14. Participation in clinical studies involving neuropsychological measures being collected more than one time per year.
15. Exclusion for FDG PET scan and amyloid imaging with florbetapir F 18: Current or recent participation in any procedures involving radioactive agents such that the total radiation dose exposure to the subject in any given year would exceed the limits of annual and total dose commitment set forth in the US Code of Federal Regulations (CFR) Title 21 Section 361.1.

Exceptions to these guidelines may be considered on a case-by-case basis at the discretion of the protocol director ([name]).

4.3 Inclusion Criteria: Follow-up Subjects

1. Must have been enrolled and followed in ADNI1 for at least one year or enrolled in ADNI-GO with original diagnosis of Cognitively Normal (CN), Mild Cognitive Impairment (MCI), or Early Mild Cognitive Impairment (EMCI) regardless of whether a diagnostic conversion has occurred since initial enrollment in ADNI.
2. Willing and able to continue to participate in an ongoing longitudinal study. A reduced battery of tests is allowable if the subject is not able/willing to complete the full battery.
3. Study partner is available who has frequent contact with the subject (e.g. an average of 10 hours per week or more), and can accompany the subject to all clinic visits for the duration of the protocol.

4.4. Exclusion Criteria: Follow-up Subjects

1. Subjects will not be able to participate in FDG PET scan and amyloid imaging with florbetapir F 18 if the following is true: Current or recent participation in any procedures involving radioactive agents such that the total radiation dose exposure to the subject in any given year would exceed the limits of annual and total dose commitment set forth in the US Code of Federal Regulations (CFR) Title 21 Section 361.1.

5. Study Procedures

The frequency of visits is dependent on the subject's original diagnosis and conversion status. Please refer to the schedule of events section in the protocol for complete details.

Visits must be conducted within 2 weeks before or after the target date. Once the visit begins, all imaging studies, biofluid collection and cognitive and clinical assessments must take place within 2 weeks from the start of the visit (as applicable). Ideally all data will be collected in-clinic. With the exception of the Screen and Baseline visit, which must be completed in-person with both the subject and study partner, follow-up visits may be conducted by telephone if there are difficulties with scheduling in-person visits. See schedule of events section of the protocol and procedures manual for details on which assessments can be done over the phone.

If subjects are not willing or able to complete the full schedule of assessments at any visit, those assessments or procedures they are willing to complete should be conducted. If subjects are no longer willing or able to travel to the clinic for visits, as much information should be collected via telephone as possible. Where there is insufficient time to complete the full in-clinic visit, the order of priority assessments is:

- Clinical Dementia Rating Scale
- ADAS-Cog
- Mini Mental State Examination
- Logical Memory I and II
- Concomitant Medications
- Adverse Events
- Diagnostic Summary
- Vital Signs

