The list of schedule of events and procedures applies to all enrolled in ADNI2 including rollovers from ADNI1 and ADNI-GO.

Timing of visits is based on cohort and conversion status:

- In-clinic visits due every year: for subjects who enrolled with an original diagnosis of EMCI, or LMCI, as well as for subjects enrolled with an original diagnosis of CN or SMC who have since converted to EMCI, LMCI or AD at any point of the study (ADNI1, ADNI-GO, or ADNI2)
- In-clinic visits are due every two years: for subjects who enrolled with an original diagnosis of CN or SMC who have NOT converted to EMCI, LMCI, or AD
- Follow-up phone call every 6 months: for subjects who enrolled at any point of the study (ADNI1, ADNI-GO, ADNI2) with an original diagnosis of AD who have provisionally consented to neuropathology or are undecided
- Note: there are no longer the 6 month interim phone checks to be conducted across any cohort, which are different than the follow-up phone calls to AD subjects who have provisionally consented to neuropathology or are undecided.

Timing of procedures conducted during in-clinic visit:

- The MRI, LP and F18 amyloid PET scan should be conducted every 2 years across originally diagnosed CN, SMC, EMCI and LMCI subjects (regardless of conversion status) until the end of ADNI2.
- MRI, LP and F18 amyloid PET scan should coincide with the scheduled in-clinic visit.
 - If the next LP and F18 amyloid PET scans are due 1 year before the next scheduled in-clinic visit (for those participants on the biennial schedule), the participant should be brought in for their in-clinic visit 1 year earlier to coincide with the timing of the LP and F18 amyloid PET scan. The MRI scan should also be conducted at this in-clinic visit. Then their subsequent in-clinic visit (which will also include PET, LP and MRI) will be 2 years from that date.
 - If the LP, F18 amyloid PET scan, and MRI scan have been occurring on alternating years all three procedures should be conducted at the next in-clinic visit (which again the in-clinic visit may need to occur 1 year early – see above). This will require 1 or 2 of the procedures to potentially be 1 year ahead of schedule. Then their subsequent in-clinic visit will be 1 or 2 years from that date based on diagnosis and conversion status.

Note: In-clinic visits may occur over several days to accommodate all study procedures.

Please contact ATRI Clinical Operations if you have further questions.

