5.1.2. Annual Visit

After May 9, 2014, the in-clinic visits will be timed according to cohort, conversion status, and when subjects are due for LP and F18 amyloid PET scans, please refer to the schedule of events section in the protocol for complete details.

In-clinic visits will be conducted annually for subjects who enrolled with an original diagnosis of EMCI, or LMCI and for subjects who enrolled with an original diagnosis of CN or SMC who has since converted to EMCI, LMCI or AD. For CN and SMC subjects who have not converted to EMCI, LMCI or AD, the ongoing in-clinic visits will be conducted every 2 years, and when LP and F18 amyloid PET scans are due. If the next LP and F18 amyloid PET scans are due before the next biennial in clinic visit, the participant should be brought in for their in-clinic visit 1 year earlier to coincide with the timing of the LP and F18 amyloid PET scan. The MRI scan should also be conducted at this in clinic visit. However, if the LP, F18 amyloid PET scan, and MRI scan have been occurring on alternating years for CN or SMC who have NOT converted to EMCI, LMCI, or AD all three assessments should be conducted at the same in clinic visit. This will require 1 or 2 of the assessments to be 1 year ahead of schedule.

THE FOLLOWING ARE MEASURED DURING THE ANNUAL VISIT

- Vital Signs
- Mini Mental State Examination
- Logical Memory I and II
- Everyday Cognition (ECog)
- Montreal Cognitive Assessment (MoCA)
- Category Fluency (Animals)
- Trails A & B
- Boston Naming Test (30-item)
- Auditory Verbal Learning Test
- Geriatric Depression Scale
- Clock drawing
- Neuropsychiatric Inventory
- ADAS-Cog 13 (with Delayed Word Recall and Number Cancellation)
- Clinical Dementia Rating Scale
- Activities of Daily Living (FAQ)
- Collection of Plasma and Serum Biomarkers
- RNA Sample Collection
- Concomitant Medications
- Adverse Events

- Diagnostic Summary
- Autopsy consent discussion

In addition to the above, the following procedures should be performed every two years:

- F18 amyloid PET scans (100%)
- CSF Collection by Lumbar Puncture (LP) (100%)
- MRI

5.2. Procedures for original diagnosis AD Subjects in ADNI2 who have provisionally consented to neuropath or are undecided

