Vital Signs*	X		X
Mini Mental State Examination*	X		X
Logical Memory I and II*	X		X
Everyday Cognition (ECog)	X		X
Montreal Cognitive Assessment (MoCA)*	X		X
Category Fluency (Animals)*	X		X
Trails A & B*	X		X
Boston Naming Test (30-item)*	X		X
Auditory Verbal Learning Test*	X		X
Geriatric Depression Scale	X		X
Clock drawing*	X		X
Neuropsychiatric Inventory	X		X
Neuropsychiatric Inventory Q		X	
ADAS-Cog 13 (with Delayed Word Recall and Number Cancellation)*	X		X
Clinical Dementia Rating Scale	X		X
Activities of Daily Living (FAQ)	X		X
Plasma and Serum Biomarker Collection* ⁴	X		X
DNA Sample Collection for GWAS (if not previously obtained)*	X		X
RNA Sample Collection*	X		X
Concomitant Medications	X	X	X
Adverse Events	X	X	X
Diagnostic Summary*	X		X
Telephone Check – Participant Status		X	
MRI Imaging (100%) ^{2*}	X		X
F18 amyloid PET scans (100%)*	X ³		X ³
FDG-PET Imaging (100%)*	X ³		X ³
CSF Collection by Lumbar Puncture (LP)(100%)*	X ³		X ³

*Assessment must be done in-person

¹ Subjects will be followed for 54 months from initial ADNI2 visit, after which they will be asked to consent to additional follow-up under a separate grant and protocol.

² All EMCI participants enrolled in ADNI-GO will continue with 3T MRI imaging. All CN and LMCI participants enrolled in ADNI1 will continue with 1.5T MRI imaging unless and until decision made by MRI Core that the site should perform 3T MRIs on all participants.

³ FDG-PET, F18 amyloid PET scans, and LP are to be performed every two years, as funding permits.

⁴ Buffy Coat is removed from plasma sample and shipped to NCRAD for genetic analysis..

1. Study Procedures

New subjects who are enrolling in this study will go through a Pre-screening and Screening period as described below. Subjects who are being followed from the first ADNI study and from ADNI-GO will continue to be seen annually in this study and contacted semi-annually via telephone. Assessments completed at each visit are listed below. Visits must be conducted within 2 weeks before or after the target date. Once the visit begins, all imaging studies, biofluid collection and cognitive and clinical assessments must take place within 2 weeks from the start of the visit. Ideally all data will be collected in-clinic. With the exception of the Screen and Baseline visit, which must be completed in-person with both the subject and study partner, if there are difficulties with scheduling follow-up visits some assessments may be done on the telephone.

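### The only anticoagulant bar on lumbar puncture is an entry criterion for new subjects; it is not carried over to rollovers and is not tied to later punctures in any cohort

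*Protocol*

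**What the plan says.** **New subjects.** Protocol Section 4.2, item 11, lists "Current use of warfarin or dabigatran (exclusionary for lumbar puncture"), under a heading that limits the list to new subjects. Exceptions to the list may be made case by case by the protocol director. Item 13 of the same list states how long it applies: "Investigational agents are prohibited one month prior to entry and for the duration of the trial". Item 11 has no such phrase. Item 15 is specific to PET: "Exclusion for FDG PET scan and amyloid imaging with florbetapir F 18: Current or recent participation in any procedures involving radioactive agents", where the resulting dose would exceed the regulatory limits.

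**Rollovers.** Section 4.4 has a single item, which repeats the PET rule: "Subjects will not be able to participate in FDG PET scan and amyloid imaging with florbetapir F 18 if the following is true". It has no LP item, and neither does Section 4.3.

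**Schedule.** The text before the schedule of events says: "The list of schedule of events and procedures applies to all enrolled in ADNI2 including rollovers from ADNI1 and ADNI-GO". It continues: "The MRI, LP and F18 amyloid PET scan should be conducted every 2 years across originally diagnosed CN, SMC, EMCI and LMCI subjects", whatever their conversion status. Section 5.1.2 lists LP among the two-yearly procedures with a target of 100%. Appendix A, for rollover visits before May 9, 2014, says: "FDG-PET, F18 amyloid PET scans, and LP are to be performed every two years, as funding permits".

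**The procedure and its risks.** Section 6.2.5 covers fasting, needle, volumes, shipment and a telephone call 24 hours after the puncture. Section 10.3 names bleeding into the CSF space among the rare risks, at much less than 1%. Neither section mentions anticoagulants or a medication check before the puncture.

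**The concern.** The sponsor judged warfarin and dabigatran use to be a reason not to perform LP and wrote that down. The rule sits in an entry list that does not govern rollovers and is not expressly tied to each puncture. A willing rollover on either drug can therefore have LP without any sentence of the protocol being broken. A new subject who starts either drug after entry is not clearly covered at a repeat LP either.

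What is at stake is participant safety rather than inference: the protocol itself names bleeding as a risk of this procedure. No error rate, power or estimate depends on the point.

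**Working it through.** The plan gives no figure to reproduce here, so the check sets the relevant sections side by side.

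1. **Where the drugs are named.** Item 11 of Section 4.2 is the only place. Sections 4.3, 4.4, 5.1.2, 6.2.5 and 10.3, and the rollover visits in Appendix A (1.2.2 and 1.2.4), contain no such rule. The only other mention of an anticoagulant is EDTA in the plasma tubes (Section 6.2.4).

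2. **Who is scheduled for LP.** All subjects with an original diagnosis of CN, SMC, EMCI or LMCI, rollovers included, every two years. Sections 5.3 and 5.5 also allow LP at a termination visit.

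3. **Safety rule by procedure, for rollovers:**

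| Procedure | Rule for new subjects | Rule that reaches rollovers |
|---|---|---|
| PET | 4.2 item 15 | 4.4, the same rule |
| MRI | 4.2 item 3 (implants, metal) | 10.2, safety screening of all subjects by MR personnel |
| LP | 4.2 item 11 (warfarin, dabigatran) | none stated |

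Of the three procedures, LP alone has no written rule that reaches rollovers.

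4. **Whether item 11 covers repeat LPs in new subjects.** It refers to current use and stands in an entry list. It can be read as applying whenever LP is due, but unlike item 13 it does not say so. The rule is therefore unclear for later LPs in new subjects and absent for rollovers.

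5. **Whether the visit record closes the gap.** Concomitant medications are recorded at in-clinic visits. No sentence links that record to withholding LP. Section 5 allows visit procedures to spread over two weeks from the start of the visit and sets no order, so the puncture may come before the medication record or days after it.

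6. **Size of the group under Section 4.4.** From the synopsis: 300 (ADNI1) + 200 (ADNI-GO) = 500 rollovers. Planned total: 650 + 500 = 1,150, so 500/1,150 = 43%. Leaving out the 150 newly enrolled AD subjects, who are no longer seen in clinic: 500/1,000 = 50%. These are planned numbers before attrition, and they count everyone under Section 4.4. The protocol gives no prevalence of warfarin or dabigatran use, so the number of subjects affected cannot be derived.

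**The case against.** The strongest reply is that the two lists differ for a reason. New subjects must agree to at least one LP (Section 4.1, item 20), so a contraindication to LP belongs in their entry criteria. For rollovers LP is not a condition of continuing (Appendix A, 1.2.2), so anticoagulant use need not affect eligibility. Section 4.4 was also not meant to list every contraindication, since the implant exclusion is missing from it too. The synopsis keeps rollovers who are no longer willing or able to have LP, and being able can include being medically able. A study physician conducts or supervises the evaluation (Section 3.1), and collection detail is left to a procedures manual that is not shown.

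Much of this stands. It explains why the rule need not exclude a rollover from the study, and it makes it likely that many clinicians would withhold LP. It does not explain why no rule governs the procedure itself. The PET item in Section 4.4 shows that a rollover can be kept in the study and barred from one procedure. Implants are covered for everyone in Section 10.2, whereas LP has no counterpart. Willingness is not suitability: Section 5 says that the procedures subjects are willing to complete should be done, and Section 3.2 aims for LP participation as near 100% as feasible.

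A reader might infer that the protocol requires LP in anticoagulated rollovers. It does not: LP is voluntary for them, depends on funding and can be withheld. A reader might also infer that new subjects are fully protected and rollovers are not. That contrast is too sharp, because item 11 does not clearly bind new subjects at repeat LPs and allows exceptions.

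**Conclusion.** The point holds as an omission with a safety consequence. The sponsor's own bar is confined to entry of new subjects, does not reach rollovers, and is not expressly applied to later LPs in any cohort. No medication check before LP is stated. It is a misplaced rule and does not contradict any other section.

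Its size is limited. About 500 planned rollovers fall under Section 4.4, but the number on warfarin or dabigatran is unknown. It would be tempting to multiply rollovers by scheduled LPs and present the product as the scale of the problem. That would count every puncture, while the gap concerns only users of the two drugs, so no such count is given. The documents also do not show that any subject was punctured while on these drugs.

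The conclusion rests on the protocol text alone. If the procedures manual already requires a check before LP in all cohorts, the practical risk is largely met, and what remains is to align the protocol with it.

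**What to change.** 1. In Section 6.2.5, state that no subject in any cohort who is currently using warfarin or dabigatran will have LP, and that current medications must be confirmed on the day of the procedure, before each LP. Reliance on the medications recorded at the visit is not enough, because that record may follow the puncture or precede it by days.
2. In Section 4.4, add an LP item in the form of the PET item: current users of either drug do not have LP but remain in the study. The reduced battery allowed by Section 4.3 already provides for this.

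The first change also settles whether item 11 of Section 4.2 binds new subjects at repeat LPs.

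The cost is a short amendment through the review boards of about 55 sites, a brief medication check on the day, and the loss of an unknown but probably small number of CSF samples. No new data collection is needed.
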